7.3.4 Safety analyses

Adverse events will be coded using the Medical Dictionary for Regulatory Activities (MedDRA) coding dictionary. Standard BI summary tables and listings will be produced. All adverse events with an onset between start of treatment and end of the residual effect period (REP), a period of 30 days after the last dose of trial medication, will be assigned to the treatment period for evaluation.

All treated patients will be included in the safety analysis. In general, safety analyses will be descriptive in nature and will be based on BI standards. No hypothesis testing is planned.

Statistical analysis and reporting of adverse events will concentrate on treatment-emergent adverse events. To this end, all adverse events occurring between start of treatment and end of the residual effect period will be considered 'treatment-emergent'. The residual effect period is defined as period of 30 days after the last dose of trial medication. Adverse events that start before first drug intake and deteriorate under treatment will also be considered as 'treatment-emergent'.

Adverse events will be graded according to CTCAE Version 4.03 and reported according to BI standards.

Serious adverse events, drug-related adverse events and adverse events of special interest will be tabulated. In addition, events leading to dose reduction or treatment discontinuation will be examined.

Frequency, severity, and causal relationship of adverse events will be tabulated by system organ class and preferred term after coding according to the current version of the Medical Dictionary for Drug Regulatory Activities (MedDRA).

Descriptive statistics will be used to describe changes in laboratory tests over time. In addition, all abnormalities of potential clinical significance will be reported. In general, potential clinical significance is defined as at least CTCAE grade 2 and an increase from baseline value by at least one CTCAE grade.

Vital signs, physical examinations, or other safety-relevant data observed at screening, baseline, during the course of the trial and at the end-of-trial evaluation will be assessed with regard to possible changes compared to findings before start of treatment.

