6. GENERAL ANALYSIS DEFINITIONS

6.1 TREATMENT(S)

Phase I

In the Phase I Part, treatments are not randomized (open-label, dose escalation). Different dose levels of the investigational medicinal product (BI 836858) can arise while combined with fixed dose of decitabine at 20 mg/m² per day. The data will be presented for all dose cohorts separately, in particular, subjects will be analysed by the dose cohort initially assigned in the first treatment course.

Table 6.1:1 Definition of analysing treatment periods

Analysing treatment period	Start date (including)	Stop date (excluding)
Screening	Date of informed consent	Date of first administration of trial medication
MTD evaluation period	Date of first administration of trial medication	First of start of the second treatment cycle or the end of the 30-day residual effect period
On-treatment	Date of first administration of trial medication	Start date of 'Follow-up'
Follow-up	Date of end of REP +1	Start date of 'Post-study'
Post-study	Last date subject status obtained / last date subject known to be alive + 1 (if subject is lost to follow-up) / date of refusal + 1 day / the date subject died + 1	During the trial: open / empty; after database lock (DBL): DBL + 1 day

Data recorded between the first administration of trial medication until up to 30 days (Residual effect period; REP) after the last administration of trial medication will be considered as on-treatment.

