7.8.1 Adverse Events

The analyses of adverse events (AEs) will be descriptive in nature. All analyses of AEs will be based on the number of subjects with AEs and NOT the number of AEs.

The analyses will be based on BI standards. Adverse events will be coded with the most recent version of MedDRA. The severity of AEs will be scaled according to CTCAE version 4.03.

Reporting will be done according to version 6 of the AE guideline ([8](#)).

For analysis of AE attributes such as duration, severity, etc. multiple AE occurrence data on the CRF, will be collapsed into AE episodes provided that all of the following applies:

- The same MedDRA lowest level term was reported for the occurrences.
- The occurrences were time-overlapping or time-adjacent (time-adjacency of 2 occurrences is given if the second occurrence started on the same day or on the day after the end of the first occurrence).
- Treatment did not change between the onset of the occurrences OR treatment changed between the onset of the occurrences, but no deterioration was observed for the later occurrence.

For each subject, all episodes with the same preferred term (PT) (system organ class, SOC) will be counted only once using a worst case approach for all AE attributes including CTCAE grading.

The analysis of adverse events will be based on the concept of treatment emergent adverse events, where a treatment emergent AE has an onset in the analysing treatment period. All adverse events occurring before first intake of trial medication will be assigned to 'screening' and all adverse events occurring after last intake of trial medication + 30 days will be assigned to 'post-treatment' (in randomized trials for listings only). For details on the treatment definition, see [Section 6.1](#). In addition, a listing will be provided, detailing the actual treatment on the day when the adverse event started.

Adverse events of special interest (AESIs):

Adverse events of special interest (AESIs) are defined in CTP Section 5.3.8.1 as infusion related reactions (IRRs) of CTCAE grade ≥ 3 , DLTs (occurring during the MTD evaluation period or repeated treatment courses), tumor lysis syndrome and drug induced liver injury (DILI).

Other significant AEs:

Other significant AEs are defined as serious and non-serious AEs that lead to dose reduction or permanent discontinuation of study medication. Their incidence will be reported by severity according to CTCAE grades.

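### SAP 7.8.1 defines treatment-emergent AEs by onset alone, omitting without declaration the protocol's clause for pre-treatment AEs that worsen on treatment; the gap affects worsening kept on one record

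*SAP*

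**What the plan says.** Protocol 7.3.4 gives two routes by which an AE becomes treatment-emergent. The first is occurrence between the start of treatment and the end of the 30-day residual effect period. The second is a deterioration clause: "Adverse events that start before first drug intake and deteriorate under treatment will also be considered as" treatment-emergent.

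SAP 7.8.1 gives only the first route: "a treatment emergent AE has an onset in the analysing treatment period". It continues: "All adverse events occurring before first intake of trial medication will be assigned to" the screening period, with no exception for later worsening. SAP 6.1 sets the on-treatment period in line with this: "Data recorded between the first administration of trial medication until up to 30 days" after the last administration.

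Deterioration enters the AE definitions of SAP 7.8.1 at one place only, the conditions for merging several occurrences of the same AE into one episode. Where treatment differs between the occurrences, they are merged only if "treatment changed between the onset of the occurrences, but no deterioration was observed for the later occurrence".

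SAP section 3 says that the plan rests on section 7 of the protocol, which contains the deterioration clause. SAP section 4, on changes to the planned analysis, declares only the cancellation of Phase II.

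**The concern.** AEs are collected from consent (protocol 5.3.9) and screening may last up to 14 days (protocol 6.2.1), so an AE can begin before first dose and still be present when treatment starts. If it then worsens, the protocol treats it as a treatment-emergent event and the SAP's wording does not. A programmer working from the SAP would follow the SAP sentence.

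The SAP rule can remove events from the on-treatment tables but cannot add any, so an error would understate treatment-emergent AEs and their worst grades. It would fall on clinical AEs such as infections and bleeding, which the SAP singles out as AE categories of their own. AE results are shown by dose cohort, and some cohorts are small.

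**Working it through.** No figure in the plan needs reproducing. The check is to apply both definitions to each way in which a worsening could be recorded.

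**Inputs.** Protocol 7.3.4 (two routes), protocol 5.3.9 (what is recorded as an AE, and from when), protocol 6.2.1 (length of screening), SAP Table 6.1:1 (screening and on-treatment are separate analysing periods), SAP 7.8.1 (onset rule, assignment to screening, collapsing conditions).

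| How the worsening is recorded | Protocol 7.3.4 | SAP 7.8.1 |
|---|---|---|
| (a) AE begins after consent and before first dose, worsens on treatment, stays on one record with its original onset date | Treatment-emergent | Screening |
| (b) Same AE, but the worsening is entered as a new occurrence dated after first dose | Treatment-emergent | Not merged, because the later occurrence deteriorated; it has an on-treatment onset and so is treatment-emergent |
| (c) Condition already present before trial inclusion, worsening on treatment and recorded as an AE under protocol 5.3.9 | Treatment-emergent | Treatment-emergent, if the recorded onset is the date of worsening |

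Row (b) takes the move from screening to the on-treatment period as a change of treatment for the collapsing rule. Table 6.1:1 supports this by listing them as separate periods.

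Only row (a) conflicts. Four conditions must hold together: onset after consent and before first dose, still present at first dose, worsening during the on-treatment period, and no second record. I found no rule in either document that tells sites to open a new record when an AE that began after consent gets worse, so row (a) is not excluded. Protocol 5.3.9 requires worsening of pre-existing conditions to be recorded, but does not settle how an AE that began during screening is to be split.

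**Size.** The documents give no count of screening AEs and no rate of worsening, so the number of row (a) events is unknown and may be zero. The effect of one misassigned patient can be stated:

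- All treated patients: 16 + 33 = 49 (protocol synopsis); 1/49 = 2.0 percentage points.
- A dose-escalation cohort at the planned minimum of 3 patients (protocol 3.1): 1/3 = 33.3 percentage points.

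**Laboratory data.** SAP 7.8.2 tabulates transitions from baseline grade to worst on-treatment grade and flags values of grade 2 or higher that rise by at least one grade. Laboratory worsening is therefore captured whatever the AE onset date. Clinical AEs have no equivalent table.

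**The case against.** The best defence is that the collapsing rule already does much of the clause's work: a deteriorated later occurrence stays separate and has an on-treatment onset. Conditions present before inclusion are baseline conditions, and protocol 5.3.9 has their worsening recorded as an AE in its own right. This stands, and it confines the problem to row (a).

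A reader might infer from the SAP wording that worsening of screening AEs is generally lost, or that a sizeable share of the 49 patients is affected because patients with active leukaemia are often unwell at screening. The documents support neither. The first overlooks the collapsing rule. The second counts illness already present before inclusion, which is a baseline condition and not a screening AE. Any percentage put on row (a) would be a guess.

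It can also be said that the AE analysis is descriptive, that DLTs are reported and tabulated separately, and that the SAP relies on company AE standards that may deal with worsening. The first two limit the consequence, and nothing here shows an effect on the MTD. The third cannot be checked from the documents, and an outside standard does not cancel an explicit SAP sentence that says otherwise.

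Finally, a date of worsening may not be recoverable from a single record. The AE items that protocol 5.3.9 gives as examples include onset, end date and severity but no date of grade change. This bears on how the fix is made, and the fix allows for it.

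**Conclusion.** The concern holds in limited form. SAP 7.8.1 and protocol 7.3.4 define treatment-emergent AEs differently, and SAP section 4 does not declare the difference although section 3 says the plan follows the protocol. This is a conflict between two stated rules and not a missing detail.

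Its effect is confined to AEs that begin between consent and first dose and worsen on one record with its pre-treatment onset date. For those, the error can only be an undercount, and the laboratory grade-shift tables do not make up for it where the AE is clinical. The number affected is unknown and may be small.

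The conclusion assumes that sites may keep a worsening on one record, which neither document rules out, and that the company standards cited in the SAP do not override its text, which cannot be verified here. It is worth correcting because it concerns the main AE tables and the change is cheap. It does not threaten the trial's primary result.

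**What to change.** In SAP 7.8.1, restore the protocol clause: an AE with onset before first trial medication whose CTCAE grade increases during the on-treatment period counts as treatment-emergent, at its worst on-treatment grade, in all on-treatment AE tables. Amend the sentence that assigns every earlier AE to screening so that it excepts these events.

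Where the eCRF holds no date of worsening, query the site before database lock so that the worsening is entered as a separate occurrence. The existing collapsing rule then keeps it as an on-treatment episode.

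The cost is one derivation, some data queries limited to AEs with onset before first dose, and AE counts that may rise slightly.

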Proprietary confidential information © 2019 Boehringer Ingelheim International GmbH or one or more of its affiliated companies

Trial period								Residual Effect Period (REP)		Extended Follow-up
Visit	Cycles ≥ 4					Cycles >7	REP		Follow-up	
	1	2	3	4 or End of Cycle	1	End of Treatment	End of REP	FU*****		
Day(s) in respective treatment cycle**)	1	2-5	8	15	22	29±3****	1	As soon as possible but not later than one week after permanent discontinuation of trial medication(s)	Not earlier than 30 days after last infusion with trial medication(s)	every 12 weeks ± 2 weeks**** (No FU visits after approval of CTP version 7.0)
DISEASE ASSESSMENT										
Disease assessment with peripheral blood and clinical assessment						x	x ¹⁹	x ¹⁹		
Disease assessment with BM aspirate (and biopsy if indicated) Separate portion of BM samples for biomarkers ¹¹ (see Table 3 and Table 4)						x ¹²	x ¹⁹	x ^{11, 13, 19}		
Cytogenetics and molecular genetics ¹⁴										
TRIAL MEDICATION										
Administration of decitabine intensive treatment (starting in Cycle 1 with treatment on 10 consecutive days)	x	x								
Administration of decitabine standard treatment (starting in Cycle 1 with treatment on 5 consecutive days)	x	x					x			
Administration of premedication ¹⁷	x		x	x	x		x			
Administration of BI 836858 ^{17, 18} (for details on BI 836858 administration refer to Table 4.1.3.1:2 and 4.1.3.2:1)	x		x	x	x		x			
Eligibility check for (further) drug administration of BI 836858	x		x		x	x	x			

Trial Protocol

Proprietary confidential information © 2019 Boehringer Ingelheim International GmbH or one or more of its affiliated companies

- *) The planned duration of a treatment cycle is 28 days. Day 1 of each cycle is defined as the day when the first dose of decitabine in that cycle is administered. The start of the next cycle must not be earlier than Day 29 of the previous cycle. There will be a maximum of 4 administrations of BI 836858 in one treatment cycle (with the exception of treatment Cycle 1, where there is a maximum of 3 administrations of BI 836858). All assessments should be performed prior to dose administration on dosing days, unless otherwise specified.
- **) Days are calculated as calendar days. Please refer to [Section 6.2](#) for details on time windows for visits and individual study procedures or assessments.

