4.1.4 Drug assignment and administration of doses for each patient

BI 836858 and decitabine will be prepared according to the instructions provided in the ISF and administered as an intravenous infusion under the supervision of the Investigator or designated personnel.

Decitabine will be administered according to [Sections 4.1.3.1](#) and [4.1.3.2](#) depending on the phase and part of the trial in which the patient is being treated.

BI 836858 will be administered as weekly i.v. infusions in 28-day cycles in combination with daily infusion of decitabine 20 mg/m^2 as per the defined decitabine treatment schedule (with the exception of treatment Arm 2 in Phase II where patients will be treated with decitabine monotherapy). BI 836858 will be administered on Days 1, 8, 15 and 22 from Cycle 2 onwards. In Cycle 1 BI 836858 will be administered on Day 8 and Day 9, Day 16 and Day 23 if WBC is $< 10 \times 10^3/\mu\text{L}$ on Day 8. In case WBC is $\geq 10 \times 10^3/\mu\text{L}$ on Day 8 (or Day 9 at the latest) of Cycle 1, the patient will not be treated with BI 836858. WBC from blood sample collected one day prior to the planned start of treatment with BI 836858 is acceptable in order to allow sufficient time for treatment decision, IRT and pharmacy logistics, as well as for preparation and delivery of the infusion. In case the platelet count prior to the 1st planned infusion with BI 836858 on Day 8 (or Day 9 at the latest) is not $\geq 25,000/\mu\text{L}$, the patient must be transfused to at least 25,000 platelets/ μL .

Whenever possible, BI 836858 should be administered in weekly intervals, i.e. two consecutive infusions should be 7 days apart. Should any unanticipated circumstances arise that might require more flexibility in the treatment schedule in order to ensure patient safety and allow patients to continue treatment within the trial, the following exceptions are acceptable and won't be classified as protocol violations: The minimum duration between two administrations of BI 836858 is 5 days and the maximum duration is 10 days. Should the need arise to deviate from the weekly administration schedule, every attempt should be made to bring the patient back to the initial schedule in order to align with the 28-day decitabine administration cycles. It is not acceptable to have more than 4 administrations of BI 836858 within any treatment cycle.

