2 and subsequent courses should be performed as clinically indicated. The actual date and time of the blood samples should be recorded in the electronic Case Report Form.

Blood sampling to screen for laboratory evidence of TLS should include:

Haematology: haemoglobin, white blood cell count (WBC) with differential and blast count, platelets (PLT)

Biochemistry: uric acid, potassium, calcium, inorganic phosphate, lactate dehydrogenase (LDH), creatinine, urea

An additional safety laboratory will be collected on Day 10 of Cycle 1 (i.e. approximately 24 h after start of the first administration of BI 836858). Other laboratory tests to be included: haptoglobin and direct antiglobulin test. Non pre-existing abnormal laboratory values (CTCAE grade 3 or higher) will be followed up every 48 h until these laboratory values are back to at least CTCAE grade 1.

In case an administration is delayed due to an AE, the patient should visit the site at least once a week for assessment of safety laboratory and AEs. More frequent visits may be appropriate as assessed by the Investigator.

[REDACTED]

5.3.7 **Electrocardiogram (ECG)**

A 12-lead resting ECG will be performed in all patients according to the schedule in the [Flow Chart](#). The ECG will be assessed for pathological results (to be recorded as either concomitant disease or AE) by the Investigator. Additional examinations should be done whenever the Investigator deems necessary.

5.3.8 **Assessment of adverse events**

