	PT Enterocolitis viral 10061841	
	PT Colitis 10009887	
	PT Enteritis 10014866	
Acute febrile neutrophilic dermatosis	PT Acute febrile neutrophilic dermatosis 10000748	

¹ A BIcMQ has been requested, however, as long as this is not available the terms as defined in Table [7.8.1:2](#) will be used.

Table 7.8.1:2 User-defined (sub-) search category of “Cardiac Failure”

Selected PTs for Cardiac Failure
Cardiac asthma
Cardiac failure

Table 7.8.1:2 User-defined (sub-) search category of “Cardiac Failure” (cont.)

Selected PTs for Cardiac Failure
Cardiac failure acute
Cardiac failure chronic
Cardiac failure congestive
Cardiac failure high output
Cardiac index decreased
Cardiac output decreased
Cardiogenic shock
Cardiomegaly
Cardiothoracic ratio increased
Dilatation ventricular
Left ventricular failure
Low cardiac output syndrome
Right ventricular failure
Oedema due to cardiac disease
Left ventricular dysfunction
Ejection fraction decreased
Cardiopulmonary failure
Diastolic dysfunction
Cardiac ventriculogram right abnormal
Cardiac ventriculogram abnormal
Cardiac ventriculogram left abnormal
Cardiac cirrhosis
Right ventricular dysfunction
Ventricular dysfunction
Cardiac resynchronisation therapy
Ventricular failure
Acute left ventricular failure
Acute right ventricular failure
Chronic left ventricular failure
Chronic right ventricular failure
Myocardial depression
Ventricular dyssynchrony
Systolic dysfunction
Neonatal cardiac failure

UDAEC will be summarized by dose cohort, search categories and preferred terms, and CTCAE grade. Some events contribute to more than one UDAEC. Patients with such AEs are counted in each of the UDAEC but are counted only once in the overall number of patients with an AE in any UDAEC.

[Tumor Lysis Syndrome](#)

In patients with a high tumor burden who are exposed to a highly effective therapy, there is a risk of rapid tumor destruction resulting in Tumor Lysis Syndrome (TLS).

Patients will be identified as having potential Tumor Lysis Syndrome if they met **both** of the following two criteria:

- (1) Two or more of the laboratory parameters meet the criteria in [Table 7.8.1:3](#),
 - a. time window
 - i. on the day of BI 836858 infusion or the following 6 days,
 - ii. at least two of the qualifying lab values must have occurred with the same 24 hour period
- (2) Have an adverse event identified by any of the SMQ in [Table 7.8.1:4](#) or have a qualifying creatinine value

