 - a. Time windows: AE onset or creatinine observation at any time during the treatment or residual effect periods

Table 7.8.1:3 Laboratory Signs of Cell Destruction

Laboratory parameter	Abnormal value
Uric acid	$\geq 476 \mu\text{mol/L}$ AND increase from relative baseline ¹ by $\geq 25\%$
Potassium	value $\geq 6.0 \text{ mmol/L}$ AND relative baseline $< 6.0 \text{ mmol/L}$
Inorganic phosphate	$\geq 1.45 \text{ mmol/L}$ AND increase from relative baseline by $\geq 25\%$
Calcium	$< 7 \text{ mg/dL}^2$ AND decrease from relative baseline by $\geq 25\%$

¹Relative baseline is derived separately for each BI 836858 infusion as the last value prior to that BI 836858 infusion. Relative baseline will be derived independently for the four parameters, ie. four baseline values do not necessarily have to be derived from the same laboratory assessment.

²For calcium, $0.25^* \text{ mg/dL} = \text{mmol/L}$

Table 7.8.1:4 Clinical Signs of Cell Destruction

Criterion
TLS broad SMQ [20000219]

Table 7.8.1:4 Clinical Signs of Cell Destruction (cont.)

Criterion
Torsade de point/QT prolongation broad SMQ [20000001]
Cardiac arrhythmia terms broad SMQ (incl bradyarrhythmias and tachyarrhythmias) [20000050]
Convulsions broad SMQ [20000079]
Creatinine Absolute increase from relative baseline by 26.5 µmol/L AND increase from relative baseline by $\geq 50\%$

For AEs during the post-treatment period, only subjects with drug related serious adverse event and protocol-specified AEs of special interest by treatment will be presented in listing.

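### The SAP's laboratory window for potential tumour lysis syndrome closes one day before the next weekly pre-dose sample, which then becomes the new baseline, so a change first seen there cannot count

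*SAP*

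**What the plan says.** SAP 7.8.1 (Tumor Lysis Syndrome) flags a patient as having potential TLS when two criteria are both met.

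- **Criterion (1), laboratory.** At least two of uric acid, potassium, inorganic phosphate and calcium must meet Table 7.8.1:3, with values taken "on the day of BI 836858 infusion or the following 6 days"; in addition, "at least two of the qualifying lab values must have occurred with the same 24 hour period". Footnote 1 to the table derives the relative baseline afresh for every infusion, as the most recent result before it.
- **Criterion (2), clinical.** An adverse event in one of four broad SMQs, or a qualifying creatinine value, is enough. Its time window is "AE onset or creatinine observation at any time during the treatment or residual effect periods".

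The protocol sets the timing of infusions and samples:

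- Section 4.1.4: "two consecutive infusions should be 7 days apart" whenever possible, but "The minimum duration between two administrations of BI 836858 is 5 days and the maximum duration is 10 days". For the first cycle: "In Cycle 1 BI 836858 will be administered on Day 8 and Day 9, Day 16 and Day 23".
- Flow Chart footnote *: "All assessments should be performed prior to dose administration on dosing days, unless otherwise specified".
- Flow Chart footnote 6: routine safety laboratory work may be done up to 2 days before the next scheduled infusion.
- Section 5.3.6.1: extra TLS samples in Cycle 1 follow Table 1; TLS sampling in course "2 and subsequent courses should be performed as clinically indicated".

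**The concern.** The window length, the weekly interval, the pre-dose sampling rule and the baseline reset do not fit together. The routine weekly sample falls one day after the window closes and is then used as the reference for the next infusion. Whether a laboratory change counts can depend on whether a site draws blood the day before dosing or on the morning of dosing.

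TLS of any grade is an adverse event of special interest, and the protocol's amendment log gives a fatal TLS case as the reason for splitting the first dose. This is the SAP's only TLS definition that uses laboratory values. The parameters of particular interest in SAP 7.8.2 include potassium and creatinine but not uric acid, phosphate or calcium. With 16 + 33 = 49 Phase I patients, shown by dose cohort, one patient classified differently visibly changes a cohort's figure.

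**Working it through.** The plan gives no figure for this rule, so there is none to reproduce. The check is date arithmetic on the nominal schedule.

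**Step 1: is the next pre-dose sample inside the window?** The window covers day 0 to day +6. With a gap of g days between infusions, the next pre-dose sample is at +g and is inside only if g ≤ 6.

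| Infusion | Next infusion | Gap (days) | Next pre-dose sample inside? | Other scheduled samples inside |
|---|---|---|---|---|
| Cycle 1 Day 8 | Day 9 | 1 | yes | Day 10 |
| Cycle 1 Day 9 | Day 16 | 7 | no | Day 10 |
| Cycle 1 Day 16 | Day 23 | 7 | no | none legible; Table 1 times not available here |
| Cycle 1 Day 23 | Day 29 at the earliest | 6 | yes | Day 24 |
| Later cycles, Day 1 | Day 8 | 7 | no | Days 2-5 appear marked in Cycles ≥ 4 |
| Later cycles, Day 8 | Day 15 | 7 | no | none established |
| Later cycles, Day 15 | Day 22 | 7 | no | none established |
| Later cycles, Day 22 | Day 29 | 7 | no | end-of-cycle visit (Day 29 ± 3) if done on Days 26-28, i.e. +4 to +6 |

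The extracted Flow Chart row for Cycles 2-3 is misaligned, so further samples between the weekly visits cannot be ruled out there.

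**Step 2: can the +7 sample count for the new infusion instead?** It is taken on that infusion's day 0, but it is also that infusion's relative baseline. Its change is 0%, so the 25% conditions fail. For potassium, one value cannot be both at least 6.0 mmol/L and, as its own baseline, below 6.0. The sample qualifies for neither infusion.

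**Step 3: effect on the next infusion.** Assumed values, for illustration only:

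- Uric acid from 350 to 500 µmol/L: 500/350 − 1 = 42.9%, and 500 ≥ 476. It would qualify against the earlier baseline. After the reset, 1.25 × 500 = 625 µmol/L is needed; against the earlier baseline it was max(476, 1.25 × 350 = 437.5) = 476.
- Phosphate from 1.1 to 1.6 mmol/L: 1.6/1.1 − 1 = 45.5%, and 1.6 ≥ 1.45. After the reset, 1.25 × 1.6 = 2.0 mmol/L is needed; before, it was max(1.45, 1.25 × 1.1 = 1.375) = 1.45.
- Potassium of 6.0 mmol/L or more before dosing: the baseline condition then fails, so no later potassium value can qualify for that infusion.

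Drawn together on day +5 or +6, as footnote 6 allows, the uric acid and phosphate values above would satisfy criterion (1).

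**Step 4: permitted intervals other than 7 days.** Full calendar days in no window = max(0, g − 7): none for g = 5, 6 or 7, then 1, 2 and 3 for g = 8, 9 and 10. At g = 5 or 6 the pre-dose sample is inside the earlier window and can count.

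**Step 5: the clinical window.** SAP Table 6.1:1 starts the on-treatment period at the first dose of any trial medication, which is decitabine on Day 1, while BI 836858 starts on Day 8 (protocol 4.1.3). The period ends 30 days after the last dose. If that last dose is a BI 836858 infusion on Day 22 of Cycle c, the length is 28(c − 1) + 22 + 30 days: 136 for c = 4 and 192 for c = 6. An event before any BI 836858, or months after the laboratory change, therefore satisfies criterion (2). Footnote 1 defines relative baseline for the four laboratory parameters only, so no reference infusion is named for creatinine.

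**The case against.** The strongest reply is that little rests on this rule. It screens for potential cases. TLS of any grade is reported and tabulated as an adverse event of special interest, and Table 7.8.1:1 has a TLS category built from the same four SMQs with no laboratory condition. Potassium and creatinine also appear in the worst-grade and shift outputs. No dose-limiting toxicity or MTD rule uses the count. All of this stands. A reader might infer that a TLS case seen by the investigator could go uncounted, or that this is the SAP's only TLS count; the documents support neither.

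The second reply concerns reach. A reader might conclude that every sample from Cycle 2 on is lost, or that Cycle 1 TLS is missed. The documents do not show this. Cycle 1 has samples inside the window on Days 10, 24 and 29 and mandatory TLS times in Table 1, which could not be read here. Cycles ≥ 4 appear to have laboratory work on Days 2-5, early draws are allowed, and the pre-dose rule yields where another time is specified. These samples make it less likely that a change is first seen at +7. They do not make the +7 sample assessable.

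The third reply is that a permissive clinical arm behind a demanding laboratory arm is a reasonable design for a screen. That also stands. The documents give neither a rate for chance events nor a source for any fixed limit between the laboratory change and the event, so a claim that the rule overcounts by a known amount is unsupported.

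**Conclusion.** The laboratory part holds. On the nominal 7-day schedule, a pre-dose sample on the next infusion day can count for neither infusion, and an abnormal value there makes the rule harder to meet afterwards. Nothing in either document repairs this. The conclusion rests on the SAP's wording, exact weekly dosing and samples drawn on the dosing day; it does not apply when the interval is 5 or 6 days or the sample is drawn 1 or 2 days early.

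The size is limited. The loss is partial and weighs most on mid-cycle weekly infusions from Cycle 2 on, where extra TLS sampling is only as clinically indicated. The number of patients affected cannot be derived from the documents. The defect lowers the sensitivity of a supplementary screen; it does not compromise TLS reporting as a whole. It is still worth correcting because the event is of special interest and the remedy uses data already collected.

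The missing time link in criterion (2) is a secondary matter of interpretation. A flagged patient's clinical event may have nothing to do with the laboratory change, and the planned rule does not show which cases are of that kind.

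**What to change.** In SAP 7.8.1, let the laboratory window for each BI 836858 infusion run up to and including the last sample before the next infusion, to a maximum of 10 days, and compare those values with the relative baseline of the earlier infusion. The 10-day cap matches the longest permitted interval and also closes the window when the next infusion comes later than that. Each pre-dose sample can then count as a result for the earlier infusion while still serving as baseline for the next. On the nominal schedule this makes the dosing-day samples on Cycle 1 Days 16 and 23, and on Days 8, 15, 22 and 29 of later weekly cycles, assessable.

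For criterion (2), keep the present time rule as the screen. Add a listing that gives, for each flagged patient, the dates of the infusion, the qualifying laboratory pair and the clinical event, with the intervals between them. State which infusion supplies the creatinine baseline. Do not impose a fixed 7-day limit.

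The cost is SAP wording and programming, with no new data or patient procedures. Expect slightly more laboratory flags.
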